7.7. Prompt Reporting of Serious Adverse Events

Once the investigator determines that an event meets the protocol definition of an SAE, he or she must notify the medical monitor within 24 hours.

ANY SAE OR ANY OUTCOME OF DEATH DUE TO ANY CAUSE, WHICH OCCURS DURING THE COURSE OF THIS STUDY, REGARDLESS OF RELATIONSHIP TO STUDY MEDICATION, MUST BE REPORTED IMMEDIATELY (within 24 hours).

COMPLETE THE SAE DETAILS REPORTING FORM AND FORWARD BY E-MAIL TO THE MEDICAL MONITOR AND THE FOLLOWING CONTACT:

[name]
Medical Safety Monitor
[contact]
E-mail: [contact]

In the initial e-mail, the investigator must provide the following CRF pages, completed to the greatest extent possible:

- AE record
- medical history
- prior and concomitant medications

Also, the following documents are to be forwarded: any laboratory results, diagnostic test results, or medical reports relevant to the SAE.

E-mail transmission is the preferred method to transmit SAE information. In rare circumstances and in the absence of e-mail capacity, notification by fax or telephone is acceptable, with a copy of the SAE reporting form and CRF pages sent by overnight mail. Initial notification via telephone does not replace the need for the investigator to complete the SAE reporting form and CRF pages within the time frames outlined.

If the investigator does not have all information regarding an SAE, he or she must not wait to receive additional information before notifying the medical monitor of the event. The form must

be updated when additional information is received. Follow-up information received on all SAEs must be forwarded to the medical monitor by using the same procedure and timelines as for an initial report.

7.8. Regulatory Reporting Requirements

The investigator must promptly report all SAEs in accordance with the procedures detailed in [Section 7.7](#), “Prompt Reporting of Serious Adverse Events.” The investigator/medical monitor has a legal responsibility to notify, as appropriate, both the local regulatory authority and other regulatory agencies about the safety of a product under clinical investigation. Prompt notification of SAEs by the investigator to the appropriate project contact for SAE receipt is essential so that SSARs that are either unexpected or observed with increasing occurrence, be reported and legal obligations and ethical responsibilities regarding the safety of other subjects are met.

An investigator letter is prepared for any SAR that is attributable to study medication, serious, and unexpected. The purpose of the investigator letter is to fulfill specific regulatory and Good Clinical Practice (GCP) requirements regarding the product under investigation.

The investigator, or responsible person according to local requirements, must comply with requirements related to the reporting of SAEs to the IRB or IEC.

8. SAFETY MONITORING PLAN

The Independent Safety Monitoring for Pneumonia Urease Positive Organism Screening Protocol (#16-327)

8.1. Background

A Safety Monitoring Committee (SMC), comprising the Independent Medical Monitor (or designee) and each Principal Investigator (or designee) will provide ongoing safety surveillance of the study. This committee will be responsible for monitoring study conduct and safety data.

The SMC will review the safety experience of each subject and the cumulative occurrences of adverse events. Through regularly scheduled and ad hoc meetings or teleconferences, the SMC will provide ongoing review of safety data to determine whether subject entry and treatment are appropriate, whether the protocol meets appropriate needs for safety monitoring and conduct, and whether continued study conduct is justified. The Clinical study site Principal Investigator will be notified accordingly when actions in response to safety concerns or protocol modifications occur and should ensure that the IRB is notified in a timely manner.

8.2. Purpose

Provide independent review and surveillance of adverse effects observed after subject exposure to a nebulized urea solution (test article) used as a tool to screen for urease positive organisms in subjects presenting with clinical signs and symptoms of pneumonia.

8.3. Assessment Personnel

A qualified Independent Medical Monitor will be a physician experienced in the assessment of lower respiratory infections, and use of nebulized solutions in such patients, and with sufficient training and experience to evaluate the safety associated with of use of the test article in these subjects.

For this program, one or more physicians from the institution who are not involved in the enrollment or assessment of study subjects, but who are Board Eligible or Board Qualified in EM, Critical Care, or Pulmonology will review subject case reports to evaluate adverse events which may or may not be related to administration of test article per the schedule described below, and advise on the safety of continued subject enrollment. For this study, [name] has agreed to be the independent medical monitor ([Section 7.7](#)).

8.4. Planned Review Process

Frequency: Greater than 100 subjects have had the test article administered to date without the occurrence of serious adverse effects (SAEs). Therefore, this protocol intends for the safety monitoring review to be performed in cohorts as follows:

- Subjects #1 through 3 = Group 1
- Subjects #4 through 6 = Group 2
- Subjects #7 through 10 = Group 3

- Subjects #11 through 15 = Group 4
- Subjects #16 through 20 = Group 5
- Subjects #21 through 25 = Group 6
- Subjects #26 through 30 = Group 7
- Subjects #31 through 35 = Group 8
- Subjects #36 through 45 = Group 9
- Subjects #46 through 55 = Group 10
- Subjects #56 through 65 = Group 11
- Subjects #66 through 75 = Group 12

Each group of subjects will be reviewed to assess whether any SAEs or other significant safety events have occurred. Safety review will be documented using the study safety review form provided in [Appendix C.1](#), to be completed by the independent medical monitor (or appropriate designee) and acknowledged by the study investigator. If an SAE has occurred, the independent medical monitor will evaluate whether the observed SAE is definitely or possibly related to test article administration, or if there is no likely relationship between the SAE and test article.

9. STATISTICAL METHODOLOGY

9.1. Determination of Sample Size

The sample size for this study was selected based on prior exposures and existing safety data. Descriptive statistical analysis of results are planned as Findings from this study will be used in order to appropriately determine the sample size requirements for future definitive evaluations of inhaled ¹³C-urea in an adequately powered study of efficacy in this population.

9.2. Study Endpoints

9.2.1. Efficacy Endpoints

Efficacy endpoints will include the following:

- Evaluate the exhaled ¹³CO₂ levels at each time point post-nebulization
- Evaluate the relationship between the exhaled ¹³CO₂ levels at each time point and subject's causative pathogen based upon sputum culture or NGS analysis
- Evaluate the sensitivity and specificity of the ¹³C-urea breath test for urease producing pathogens
- Evaluate the positive and negative predictive value of the ¹³C-urea breath test for urease producing pathogens
- Correlation of the ¹³C-urea breath test with CURB65 in subjects with sputum cultures or NGS results positive for urease pathogens
- Correlation of the ¹³C-urea breath test with PSI in patients with sputum cultures or NGS results positive for urease pathogens
- Univariate association of all study variables with urease pathogen caused pneumonia
- Multi-variate logistic regression model for urease pathogen caused pneumonia utilizing study variables that are significant in univariate analysis to compute odds ratio for each model variable and overall explanation of variance by model

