Study populations: Intent-to-Treat (ITT) Analysis Set: The ITT set will include all subjects who receive nebulized ^{13}C -urea. The ITT analysis set is also referenced as the Safety Analysis Set. Safety analysis will be performed using the ITT set. Modified Intent-to-Treat (mITT) Analysis Set: The mITT subjects include all ITT subjects who provide at least one post-dose breath sample. Efficacy analysis will be performed on the mITT analysis set.	
Efficacy analysis: Breath test exhaled $^{13}\text{CO}_2$ results at each time point will be presented for the overall population for determination of optimal breath sampling time. Relationship between the exhaled $^{13}\text{CO}_2$ at each time and subject's pneumonia diagnosis and pathogen (determined by sputum culture or NGS) will be examined. The time point where exhaled $^{13}\text{CO}_2$ can reliably predict the presence of urease positive pathogen in subjects with pneumonia diagnosis will be considered as the optimal time for ^{13}C -urea breath test sampling. The proportion of subjects with breath test positive/negative determination will be compared to sputum culture or NGS results when available. Correlation analyses will be performed where sufficient data are available.	
Safety analysis: The Medical Dictionary for Regulatory Activities (Version 18 or higher) will be used to classify all AEs with respect to system organ class and preferred term. AEs will be summarized for the safety analysis set.	

TABLE OF CONTENTS

SYNOPSIS (PAGE 1 OF 4)	3
TABLE OF CONTENTS.....	7
LIST OF ABBREVIATIONS.....	11
1. INTRODUCTION	12
2. STUDY OBJECTIVE.....	14
3. INVESTIGATIONAL PLAN.....	15
3.1. Overall Study Design.....	15
3.2. Rationale for Study Design and Control Groups.....	16
3.3. Clinical Study Sites.....	16
4. STUDY POPULATION.....	17
4.1. Inclusion Criteria	17
4.2. Exclusion Criteria	17
4.3. Discontinuation of Subjects.....	18
4.3.1. Procedures for Withdrawal	18
4.3.2. Replacement of Subjects.....	18
4.4. Lifestyle Guidelines.....	18
4.4.1. Confinement	18
4.4.2. Diet	18
5. TREATMENTS.....	19
5.1. Administration of Study Medication	19
5.2. Identity of Study Medication	19
5.3. Method of Assigning Subjects to Treatment Groups	19
5.4. Selection of Doses	19
5.5. Selection of Timing of Dose.....	19
5.6. Blinding and Unblinding of Study Medications.....	19
5.7. Treatment Compliance.....	19
5.8. Drug Accountability	20
5.9. Packaging, Labeling, and Storage	20

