2. STUDY OBJECTIVE

The primary objective of this study is to determine the ability of the ¹³C-urea breath test to detect urease producing pathogens in patients with pneumonia as confirmed on sputum culture results.

Additional objectives of this study will include:

- Determine optimal times for post-nebulization breath collection
- Evaluate the safety and tolerability of the ¹³C-urea breath test in patients with pneumonia

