6.1.3. Processing of samples for microbiome analysis

A oropharyngeal swab and a portion of the collected sputum sample will be preserved with a nucleic acid protectant that also neutralizes infectious organisms, such as Zymo Biosciences DNA/RNA shield or equivalent. We will conduct microbial sequencing to determine the presence of microorganisms and their relative abundance. To this end, total nucleic acid (DNA and/or RNA) will be isolated to allow for microbiome analysis by sequencing. Microbiome sequencing will be done at UNM laboratories under direct supervision of the study investigators. Sequencing will be conducted on a next generation sequencing system, such as the Illumina MiSeq sequencer. The microbiome content will be determined through bioinformatic analysis of the sequencing reads with a taxonomic database such as the Greengenes Consortium Database, Kraken database or a similar microbiome classification database. These samples will be labeled with the de-identified study subject ID, the date and time of collection, and a study ID. Raw sequence data generated from the sequencer in the format of a .fastq file and labeled only with the study number and no identifying data may be transferred, stored, and analyzed using web and/or cloud-based solutions.

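### An NGS result can make a subject reference-positive, but the plan never defines a positive NGS result and gives the measured relative abundance no role in the analysis

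*Combined protocol and SAP*

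**What the plan says.** Three endpoints in Section 9.2.1 bring in NGS. The exhaled ¹³CO₂ endpoint relates levels to the "subject's causative pathogen based upon sputum culture or NGS analysis". The CURB-65 correlation is taken "in subjects with sputum cultures or NGS results positive for urease pathogens", and the PSI correlation is worded the same way for patients. The sensitivity/specificity and predictive-value endpoints refer only to the "breath test for urease producing pathogens" and name no reference standard.

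The synopsis efficacy analysis says that breath calls "will be compared to sputum culture or NGS results when available".

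Other places use culture alone. The primary objective (Section 2 and synopsis) concerns "urease producing pathogens in patients with pneumonia as confirmed on sputum culture results". Sections 3.2 and 9.5 compare the breath test with sputum culture only. The synopsis version of the CURB-65 and PSI endpoints also mentions culture only.

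Section 6.1.3 is the only account of how sequencing is processed: "We will conduct microbial sequencing to determine the presence of microorganisms and their relative abundance", and "The microbiome content will be determined through bioinformatic analysis of the sequencing reads with a taxonomic database". On specimens: "A oropharyngeal swab and a portion of the collected sputum sample will be preserved with a nucleic acid protectant". It gives no rule for turning these outputs into a positive or negative call.

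**The concern.** Sequencing returns read counts by taxon, and a positive or negative status exists only once someone sets a rule. With an either/or reference, that rule directly decides who counts as reference-positive. Two things are at stake.

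- **Timing of the rule.** The study is unblinded (Section 5.6). Breath results are reported to the principal investigator (Section 6.1.2), sequencing is supervised by the study investigators (Section 6.1.3), and study staff can link results to individual subjects (Section 10.6). Nothing stops a cut-off, taxon list or specimen from being chosen with the breath results in view.
- **Incidental detection.** If a lenient rule counts organisms that are not causing the pneumonia, subjects with no expected breath signal join the reference-positive group. Apparent sensitivity and negative predictive value fall for reasons unrelated to the test, and the CURB-65 and PSI subsets are diluted. Section 9.1 says the findings will be used to size a later efficacy study, so the distortion would carry forward.

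Relative abundance is the one planned measurement that could help separate a trace finding from a dominant organism, yet no endpoint or analysis mentions it.

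**Working it through.** **1. Nothing to reproduce.** The plan states no power, precision, prevalence or NGS-positive rate. One figure can be derived. Sputum and swab are required only in Cohort B (Appendix A), so at most 75 − 15 = 60 subjects have a required reference result.

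**2. What is left open.**

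| Element of an NGS call | Where one would look | Found |
|---|---|---|
| Abundance or read cut-off | 6.1.3, 9.2.1, 9.5 | None |
| Urease-producing taxa | 1, 3.2 | Three examples, not a closed list |
| Specimen (sputum or swab) | 6.1.3, 9.2.1 | Both sequenced, neither designated |
| Disagreement with culture | 9.2.1, 9.5, synopsis | None |
| Role of relative abundance | 9.2.1, 9.5 | None |

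**3. Illustration of size, all rates assumed.** Let p be the share of subjects with true urease-pathogen pneumonia (0.1 to 0.4), and c the share of the remainder called NGS-positive incidentally. True sensitivity is Se = 0.80 and true specificity Sp = 0.90. The reference is assumed to catch every true case, and incidental detections are assumed to give a breath-positive result only at the false-positive rate, 1 − Sp = 0.10.

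- Reference-positive share = p + (1 − p)c
- Apparent sensitivity = [p·Se + (1 − p)·c·(1 − Sp)] / [p + (1 − p)c]

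With c = 0.10:

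- p = 0.1: (0.080 + 0.009) / 0.19 = 0.47
- p = 0.4: (0.320 + 0.006) / 0.46 = 0.71

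| p | c = 0 | c = 0.10 | c = 0.25 | c = 0.50 |
|---|---|---|---|---|
| 0.1 | 0.80 | 0.47 | 0.32 | 0.23 |
| 0.2 | 0.80 | 0.60 | 0.45 | 0.33 |
| 0.3 | 0.80 | 0.67 | 0.54 | 0.42 |
| 0.4 | 0.80 | 0.71 | 0.61 | 0.50 |

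In counts out of 60 at p = 0.1 and c = 0.10, there are 6 true cases and 54 × 0.10 = 5.4 incidental ones, so nearly half the reference-positives are not cases.

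**4. Other measures under the same assumptions.** Apparent specificity stays at 0.90, but fewer subjects estimate it. At p = 0.2 the reference-negatives fall from 48 (c = 0) to 43 (c = 0.10) and 24 (c = 0.50), with exact 95% intervals 0.77–0.97, 0.78–0.97 and 0.73–0.99. Apparent negative predictive value is the true value times (1 − c). At p = 0.2 it goes from 0.72 / 0.76 = 0.947 to 0.947 × 0.90 = 0.85.

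**5. What near-universal positivity would require.** For 90% of subjects to be reference-positive, c = (0.9 − p)/(1 − p), which is 0.89 at p = 0.1 and 0.83 at p = 0.4. The documents give no value for c.

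**The case against.** The other side has four good arguments.

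- **Scope.** Only two of the eight endpoints in Section 9.2.1 speak of positive NGS results, and a third refers to NGS analysis. The primary objective and Section 9.5 rest on culture, so the main accuracy comparison may never involve NGS. This stands as a limit. It does not settle the matter, because the synopsis analysis admits NGS and the accuracy endpoints name no reference.
- **No any-read rule.** A reader might infer that, because sequencing is sensitive, almost every sputum will be positive. At an assumed 50,000 reads, a taxon at 0.01% abundance yields at least one read with probability 1 − (1 − 0.0001)^50,000 = 99.3%. That figure describes a sample already carrying the taxon and says nothing about how many subjects carry one. The plan adopts no any-read rule, and its references to causative pathogens point away from trace findings, though they are not made operational. The inference is not supported.
- **Abundance is not discarded.** A reader might also infer that the abundance data will be thrown away. The plan does not say so, and both the exhaled-level endpoint and the univariate analysis could accommodate them. They are unassigned.
- **Exploratory status.** This is a descriptive Phase 1 study with no formal hypothesis (Section 9.3.2). That lowers the consequence of the gap, but a descriptive accuracy estimate still needs a defined reference.

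**Conclusion.** The point holds in a limited form. Where the plan lets NGS define the reference, it does not say what a positive result is, and the abundance it will measure has no stated analytic use. The call can therefore be fixed after breath results are known, and incidental detection would bias accuracy downward. Under the assumptions above, 10% incidental detection takes apparent sensitivity from 0.80 to between 0.47 and 0.71. These are illustrative figures: prevalence, incidental-detection rate and true accuracy are all assumed, and the effect applies only if NGS enters the accuracy reference. Near-universal positivity is not shown. Nor is the culture-based primary comparison affected, provided the sections are reconciled so that it stays culture-based. The change should be made, since it costs little and protects estimates meant to inform a later trial.

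**What to change.** 1. **Reconcile the reference standard.** Align Sections 2, 3.2 and 9.5 and the synopsis CURB-65/PSI endpoints (culture only) with Section 9.2.1 and the synopsis efficacy analysis (culture or NGS). Keep sputum culture as the reference for the primary objective, and name it in the sensitivity/specificity and predictive-value endpoints. Report any NGS-based accuracy separately, with a cross-tabulation of culture against the NGS call so that disagreement is visible.
2. **Use the abundance.** For the endpoint relating exhaled ¹³CO₂ to NGS, analyse the summed relative abundance of listed urease-producing taxa in sputum as a continuous variable, with a rank correlation against the ¹³CO₂ change at each time point.
3. **Lock the binary call where one is needed.** Continuous abundance cannot define the CURB-65 and PSI subsets or yield sensitivity and specificity. For these, fix the specimen (sputum), the taxon list and the abundance threshold in a dated document before sequencing results are linked to breath results, and show results at two other thresholds.

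The cost is analysis-plan wording and minor bioinformatics, since relative abundance is already to be produced. There are two drawbacks. Any threshold is partly arbitrary, hence the two alternatives. Relative abundance is a share of reads, not a bacterial load, whereas Section 5.5 ties the breath signal to infection burden, so a weak correlation would not by itself count against the test.

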6.2.3. Clinical Laboratory Tests

The investigator or designee will document results of laboratory tests collected in the course of routine care during the subject's hospitalization. These results will be collected on the CRF.

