4.8 Source Document Requirements

PROTOCOL 16-327

Data entered onto CRFs must be verified against original source documents to confirm accurate, complete and legible reporting of valid data. Original source documents may be the electronic medical record at the site, or copies of select medical record documents maintained in a shadow chart, or a combination of both. Sites will use an inclusion/exclusion criteria checklist copied from the CRF when a study coordinator approaches a patient to determine eligibility for the trial and to ensure all the required presentation data are captured and documented. This checklist will be considered a source document for the required presentation data. Medical history may also be obtained on this Worksheet but must be verified with the subject's official medical record. If the subject does not have an established medical record at the study facility to verify against, it should be noted by the study site personnel in the study documents that the information was derived from a patient interview and is non-verifiable.

Additional source documents required by the study include but are not limited to:

- ◆ Study required specimen collection dates, times, and method of collection,
- ◆ Medication records including prior and prescribed antibiotics,
- ◆ Laboratory tests,
- ◆ Chest X-ray results,
- ◆ Prior non-drug therapies and procedures,
- ◆ Documentation of the Initial and Final Diagnoses, and
- ◆ Disposition of the patient

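### As worded, the logistic model for urease-pathogen pneumonia can admit predictors that define or post-date the outcome, and it does not guarantee the breath result a place

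*Combined protocol and SAP*

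**What the plan says.** Section 9.2.1 lists eight efficacy endpoints. The last two are a "Univariate association of all study variables with urease pathogen caused pneumonia" and a multivariable logistic model "utilizing study variables that are significant in univariate analysis to compute odds ratio for each model variable", with the "overall explanation of variance by model" also reported. The synopsis repeats both. Section 9.5 (Efficacy Analysis) describes neither, and no section says what counts as a study variable, what significance threshold applies, or which reference standard defines the modelled outcome. The nearest guide is another 9.2.1 bullet, which bases the causative pathogen on sputum culture or sequencing.

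The study records data well beyond the time of the breath test:
- Section 6.1.3: sequencing of sputum and an oropharyngeal swab to "determine the presence of microorganisms and their relative abundance".
- Section 6.2.3: staff "document results of laboratory tests collected in the course of routine care" during the hospital stay, on the CRF.
- Section 3.1: clinical course followed for at least 24 hours where possible, for final diagnosis and outcome.
- Section 9.2.2: death, ICU transfer or intubation, as a safety endpoint.
- Appendix E, 4.8: required source documents include "Documentation of the Initial and Final Diagnoses", patient disposition and "Medication records including prior and prescribed antibiotics".
- Appendix E, 4.2: Cohort B CRFs are completed through hospital discharge.

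**The concern.** A screen on univariate significance favours the variables closest to the outcome. Organisms found by culture or sequencing may be the outcome. A final diagnosis can be informed by the culture. Later laboratory results, disposition and ICU transfer did not exist when the breath test was read. Under the rule as written, all of these compete with the breath result for a place in the model, and nothing guarantees that the breath result is retained.

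This differs from overfitting. A predictor that carries the outcome's own information keeps its apparent strength in a larger sample, and internal validation would confirm it. At stake are two reported quantities, the odds ratios and the explained variance. Section 3.2 describes the test as a possible rapid guide to antibiotic choice. A model that conditions on later information does not address what the breath result adds at that point.

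**Working it through.** **Reproduction.** The plan gives no event count, model size, threshold or expected explained variance, so there is no figure to reproduce. The only usable number is the sample size: up to 75, of whom 15 are in Cohort A, leaving 75 − 15 = 60 in Cohort B, where sputum is required (sections 3.1 and 6.3.1).

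**What the wording admits.**

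| Recorded item | Relation to the outcome | Known at the breath test? |
|---|---|---|
| Sputum culture organism | can define it | no, result comes later |
| Sequencing organisms and abundance | can define it | no |
| Final diagnosis | can be informed by it | no |
| Laboratory results later in the stay | not stated | no |
| Disposition, ICU transfer | not stated | no |
| Demographics, history, screening vital signs | precede it | yes |

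Nothing in sections 9.2.1, 9.3 or 9.5 separates the first five rows from the last.

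**Illustration of size.** These assumptions are not in the documents: outcome prevalence 15, 25 or 35%; one binary candidate agreeing with the outcome with a set probability; selection by two-sided Fisher test at p < 0.05; explained variance as Nagelkerke R². There were 1,500 simulated trials of 60 subjects per setting. Ranges run across the three prevalences.

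| Agreement with outcome | Passes the screen | Median R² alone, n = 60 | R² at unlimited n |
|---|---|---|---|
| none (unrelated) | 3–4% | 0.01–0.02 | 0 |
| 70% | 56–81% | 0.15–0.20 | 0.14–0.19 |
| 80% | 90.5–99.8% | 0.33–0.43 | 0.32–0.41 |
| 90% | at least 99.5% | 0.61–0.69 | 0.58–0.68 |
| 100% (the outcome itself) | 100% | 1.00 | 1.00, no finite odds ratio |

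The last column uses R² = [1 − exp(2(L0 − L1))] / [1 − exp(2·L0)], where L0 and L1 are the mean log-likelihoods per subject without and with the candidate. For 25% prevalence and 80% agreement:
- Candidate present: 0.25 × 0.8 + 0.75 × 0.2 = 0.35.
- Outcome probability if present: 0.20 / 0.35 = 0.571; if absent: 0.05 / 0.65 = 0.077.
- L0 = 0.25 ln 0.25 + 0.75 ln 0.75 = −0.562.
- L1 = 0.35(0.571 ln 0.571 + 0.429 ln 0.429) + 0.65(0.077 ln 0.077 + 0.923 ln 0.923) = −0.415.
- R² = (1 − exp(−0.294)) / (1 − exp(−1.125)) = 0.255 / 0.675 = 0.38.

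The simulated median at n = 60 is also 0.38, so a larger sample would not remove the effect.

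**Weak candidates.** With 12 of 60 positive, a candidate present in 30% of positives and 15% of negatives passes in about 20% of simulated trials, with R² of 0.03 at unlimited n. The problem is material only for variables close to the outcome, such as culture, sequencing or a culture-informed diagnosis.

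**Odds ratios.** How the breath result's adjusted odds ratio would move depends on how it relates to the admitted variable within outcome groups. The documents do not allow that to be computed.

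**The case against.** No section names a predictor. A sensible analyst would not enter the culture organism to predict a culture-defined outcome, so this is a gap in specification. That is fair. A reader might infer that the planned model does predict the outcome from itself, but the documents only permit it.

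A reader might also infer that recorded treatment follows from the culture. The documents do not support this. Section 5.10 limits CRF medications to the 7 days before dosing plus drugs started for an adverse event, and section 5.5 places the breath test before, or within 4 hours after, the start of antibiotics. The reference to prescribed antibiotics is in a monitoring-plan list of source documents, not a list of analysis variables. Treatment course is discussed at the 48 to 96 hour contact (section 6.3.3), but nothing makes it a candidate or links it to the culture. Nor is ICU transfer or disposition said to be driven by the culture; the point about them is timing only.

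Finally, the analysis is exploratory: section 9.1 plans descriptive statistics, section 9.3.2 tests no formal hypothesis, and the primary objective concerns detection against sputum culture. A univariate table of later course against pathogen is legitimate description. All of this stands and limits the consequence. It does not change the rule in 9.2.1, which when followed as written sends any significant variable into the model.

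**Conclusion.** The concern holds as a specification risk. The selection rule admits outcome-defining and later variables and does not protect the breath result. If a variable close to the outcome enters, it will usually pass the screen and can dominate the explained variance at any sample size; a variable identical to the outcome gives no finite odds ratio. These sizes rest on assumed prevalence, agreement, threshold and R² measure.

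The documents do not support concluding that leakage will occur, or that sensitivity, specificity or predictive values are affected, since those do not depend on this model. Severity is minor to moderate: the model is secondary and exploratory, but its results are listed efficacy endpoints.

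**What to change.** Leave the univariate bullet in 9.2.1 and the synopsis as description. In the multivariable bullet:
- Limit candidates to variables known at or before the breath test (demographics, history, screening vital signs, imaging, CURB-65/PSI, laboratory results available in the ED), plus the breath result, and list them in advance.
- Exclude culture, sequencing, final diagnosis and later course as predictors.
- State which reference standard defines the outcome: culture, sequencing, or a stated combination.
- Keep the breath result in the model whatever its univariate p-value, and report the model with and without it.

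Section 9.5 should then describe both analyses in the same terms. The cost is wording and one additional model fit, with no new data, subjects or procedures. The reported explained variance is likely to be lower.
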